2. RATIONALE FOR THE STUDY AND FOR DOSE AND DOSING SCHEDULE

2.1. Rationale for the Study

This study is an open-label extension of Study MYK-461-004 (PIONEER-HCM) to assess long-term safety, tolerability, and efficacy of mavacamten in participants with oHCM who had previously participated in the PIONEER-HCM study.

MyoKardia has designed the current study to generate long-term data in participants with symptomatic oHCM, using an approach that conforms to established ethical standards of safe human experimentation and the requirements of Good Clinical Practice (GCP).

2.2. Rationale for Dose and Dosing Schedule

Given that the mavacamten PK parameters of each PIONEER-HCM participant are known based on mavacamten plasma concentration measurements taken during that study, an individualized mavacamten dose was computed for each participant (Table 1) to target a mavacamten plasma concentration of 250 to 500 ng/mL. These plasma concentration levels have generally been associated with a marked reduction in LVOT gradient, and they have been well-tolerated without

excessive reductions in LVEF. To maximize safety, the starting dose will be 5 mg for all participants. If applicable, a dose increase to the Target Dose will occur at Week 6 based on Week 4 determinations of LVOT gradient, LVEF, and mavacamten plasma concentration (see [Section 4](#)).

Table 1 Individualized Target Doses

Participant Identification in Study MYK-461-004	Target Dose (mg)
[REDACTED]	10
[REDACTED]	10
[REDACTED]	5
[REDACTED]	5
[REDACTED]	10
[REDACTED]	15
[REDACTED]	5
[REDACTED]	5
[REDACTED]	10
[REDACTED]	10
[REDACTED]	10
[REDACTED]	5
[REDACTED]	5
[REDACTED]	10
[REDACTED]	15
[REDACTED]	10
[REDACTED]	15
[REDACTED]	10
[REDACTED]	10
[REDACTED]	10

For eligible participants, a dose increase beyond the Target Dose at a later time point beyond Week 6 may also be possible; the Investigator first should discuss this with and get approval from the MyoKardia Medical Monitor (see [Section 4](#)).

At Week 48 and Week 72, a stress echocardiogram will be performed. If the post-exercise LVOT gradient is ≥ 50 mmHg, further dose adjustment may be considered and discussed with the MyoKardia Medical Monitor. If dose adjustment occurs at Week 24 or beyond, a follow-up visit should be scheduled 4 weeks later (± 7 days) to include a transthoracic echocardiography (TTE) assessment.

Dose adjustment may also take place beyond Week 6 based on results of TTE, stress echocardiography and/or PK evaluation, and based upon the opinion of the Investigator in conjunction with the MyoKardia Medical Monitor.

The Investigator, in conjunction with the Medical Monitor, may also elect to dose reduce a participant after they are on a stable dose of 10 or 15 mg mavacamten for 24 weeks or longer. Participants that have been dose reduced will undergo a follow-up visit 4 to 8 weeks (± 7 days) later (to mirror Week 8 assessments, including a TTE assessment). Based on results and clinical symptoms at follow-up visits, subsequent dose decisions will be discussed with the MyoKardia Medical Monitor. This cycle of potential dose reduction and follow-up can be repeated more than once (after at least 24 weeks on a stable dose of 10 or 15 mg treatment) and will need to be discussed with the MyoKardia Medical Monitor each time before it is carried out.

3. STUDY OBJECTIVES

3.1. Primary Objective

The primary objective of this study is:

- To assess the long-term safety and tolerability of mavacamten in individuals with symptomatic oHCM

3.2. Secondary Objectives

The secondary objectives of this study are to assess in individuals with symptomatic oHCM the long-term effect of mavacamten on:

- LVOT obstruction
- Functional capacity
- oHCM symptoms

3.3. Pharmacokinetic Objective

The PK objective of this study is:

- To perform population PK analyses in individuals with symptomatic oHCM receiving mavacamten

4. OVERALL STUDY DESIGN AND PLAN

[figure not shown]
This is a Phase 2, open-label extension, multicenter study of individuals with symptomatic oHCM who completed Study MYK-461-004 (PIONEER-HCM).

Participants in this study will be screened to ensure they continue to meet eligibility criteria. Participants are allowed to stay on background therapy with either beta blockers or calcium channel blockers provided they have been on a stable dose for at least 14 days prior to Screening. Once enrolled into Study MYK-461-008, participants will undergo baseline assessments and

receive mavacamten QD for a duration of up to approximately 5 years (Figure 1) or until mavacamten becomes commercially available (at the discretion of MyoKardia).

The starting dose will be 5 mg. Participants will return at Week 4 for a plasma PK sample to measure drug levels and for an echocardiogram to determine LVOT gradient at rest and after exercise as well as to measure LVEF. If mavacamten clinical development is discontinued, this study will be terminated. The end of study (EOS) is defined as the date of the last observation of the last participant.

Figure 1 Study Schema

Telehealth Visits: Weeks 18, 30, 42, 54, 66, 78, 90, 102, 114, 126, 138, 150, 162, 174, 186, 198, 210, 222, 234, and 246

Abbreviations: EOS, end of study; ET, early termination; EOT, end of treatment; NT-proBNP, N-terminal pro B-type natriuretic peptide; PK, pharmacokinetic blood sample taken; QD, once daily; TTE, transthoracic echocardiogram.

Note: Dose reduction rule applies throughout.

Note: For all females of childbearing potential, a pregnancy test will be taken every 4 weeks at home when no clinic visit is scheduled.

^a Dose adjustment to individual targeted dose: dose calculated to achieve mavacamten plasma concentration of 250-500 ng/mL in each participant. Dose adjustment may also take place beyond Week 6 based on results of TTE/stress echocardiogram and PK evaluation and based upon the opinion of the Investigator in conjunction with the MyoKardia Medical Monitor. Dose adjustments beyond the previous Target Dose may only be exceeded for each given participant following discussion between the Investigator and the MyoKardia Medical Monitor. Lower doses are permissible.

^b Includes a stress TTE at Screening (Baseline), Weeks 4, 48, 72, 156, 204, 252/EOT, and 260/EOS. These are in addition to resting and post-Valsalva TTEs at all visits indicated with a vertical arrow.

Dose adjustment may occur at Week 6 based on Week 4 assessments. Target dosing will be individualized for each participant based on his or her PK data obtained in the MYK-461-004 study (Table 1). Specifically, the Target Dose for each participant is the dose associated with a steady-state trough plasma concentration of approximately 250 ng/mL to 500 ng/mL, and the Target Dose for a given participant may not exceed the dose (unless previously discussed between the Investigator and the MyoKardia Medical Monitor) as detailed in Table 1, although

lower doses are permissible. Participants will return at Week 6 for the results and dose adjustment. Note that at Week 4, the LVOT gradient will be measured at rest with Valsalva maneuver and post-exercise. If the LVOT gradient post-exercise is < 30 mmHg, then the dose will not be increased at Week 6.

The dose may be increased at Week 6 to the Target Dose provided in [Table 1](#) unless one or more of the following criteria are met at Week 4:

- LVEF is $< 55\%$, and/or
- LVOT gradient is < 30 mmHg after exercise, and/or
- Trough mavacamten plasma concentration is > 350 ng/mL, and/or
- A dose increase is not warranted in the clinical judgment of the Investigator

Note: if a participant is eligible for a dose increase at Week 6 but the dose is not increased due to Investigator judgment, a dose increase to the participant's Target Dose at a later time point beyond Week 6 may be possible; the Investigator should first discuss this with and get approval from the MyoKardia Medical Monitor.

For eligible participants, a dose increase beyond the Target Dose at a later time point beyond Week 6 may also be possible; the Investigator first should discuss this with and get approval from the MyoKardia Medical Monitor.

If one or more of the above 4 criteria are present, no dose increase will occur. Also, a dose decrease or discontinuation may be instituted at Week 6 or at any other visit according to the dose reduction rule described below.

Participants who have had a dose adjustment (either in mavacamten or background cardiomyopathy therapy) should return to the clinic approximately 28 days later (± 7 days) for an unscheduled visit with resting TTE to confirm safety. Repeat of post-exercise echocardiographic assessment of LVOT gradient will be at the Investigator's discretion. Based on results and clinical symptoms at follow-up visits, subsequent dose adjustments will be discussed with the MyoKardia Medical Monitor.

Dose Reduction Rule: The dose may be reduced or discontinued in the case of an exaggerated pharmacologic effect at any time during the study based on the clinical judgment of the Investigator.

If results as reported by the central laboratories from any visit show mavacamten plasma concentration is ≥ 1000 ng/mL, or LVEF $< 50\%$ (as read by site), or Fridericia-corrected QT interval (QTcF) meets the following criteria, the participant will be notified by the study site/Investigator with further instructions:

- If QRS is narrow (< 120 milliseconds), then temporary discontinuation criteria are the smaller of: 15% increase from baseline QTcF OR QTcF ≥ 520 milliseconds
- If QRS is wide (≥ 120 milliseconds), then temporary discontinuation criteria are the smaller of: a 15% increase from baseline QTcF OR QTcF ≥ 550 milliseconds

Dosing with study drug will be immediately stopped and the following procedures implemented:

- If the participant is taking 5, 10, or 15 mg, study drug will be temporarily discontinued and he or she will return for an unscheduled visit (with electrocardiogram [ECG] and TTE assessments) 2 to 4 weeks later
- If LVEF $\geq 55\%$ (as read by site) and QTcF < 500 milliseconds at the unscheduled visit, then the study drug will be restarted at a lower dose, as shown below (previous dose \rightarrow restart dose):
 - 5 mg \rightarrow resume 5 mg
 - 10 mg \rightarrow 5 mg
 - 15 mg \rightarrow 10 mg

Participants on 5 mg who have been temporarily discontinued on treatment based on clinical evaluation can be considered for dose reintroduction at 5 mg following agreement between the Investigator and the MyoKardia Medical Monitor.

If LVEF (as read by site), plasma drug concentration, and/or QTcF persist out of range at the follow-up visit, then the participant will be discontinued from the study.

The Investigator, in conjunction with the Medical Monitor, may also elect to dose reduce a participant after they are on a stable dose of 10 or 15 mg mavacamten for 24 weeks or longer. Participants that have been dose reduced will undergo a follow-up visit 4 to 8 weeks (± 7 days) later (to mirror Week 8 assessments, including a TTE assessment). Based on results and clinical symptoms at follow-up visits, subsequent dose decisions will be discussed with the MyoKardia Medical Monitor. This cycle of potential dose reduction and follow-up can be repeated more than once (after at least 24 weeks on a stable dose of 10 or 15 mg treatment) and will need to be discussed with the MyoKardia Medical Monitor each time before it is carried out.

After Week 6, additional clinic visits will occur at Week 8 (± 7 days), Week 12 (± 7 days), and every 12 weeks (± 7 days) thereafter. Between clinic visits, participants will also be contacted by phone at Week 18 and every 12 weeks thereafter. An EOS visit will occur 8 weeks (± 7 days) after the last administration of study drug. Visits will entail recording vital signs, targeted physical examination, ECG, safety laboratory tests, NT-proBNP, adverse events (AEs), NYHA functional class, Kansas City Cardiomyopathy Questionnaire (KCCQ) score, and concomitant medications, as detailed in [Table 2](#) and [Table 3](#). Predose blood samples for assessment of drug concentrations will be performed at the visits indicated in [Table 2](#) and [Table 3](#). Resting and post-Valsalva TTEs and stress TTEs to determine post-exercise LVOT gradient will be performed at baseline and post-baseline, as indicated in [Table 2](#) and [Table 3](#). For females of childbearing potential, pregnancy testing will be performed in the clinic or at home every 4 weeks.

Participants will be followed through completion of EOS procedures. All AEs, including SAEs, will be collected from the time of informed consent through the duration of the study, up to and including the EOS visit. If there is a significant clinical abnormality or clinically significant laboratory abnormality in need of monitoring, the participant will be followed until resolution of the abnormality or until it is considered stable in the opinion of the Investigator.

In the context of COVID-19 or other pandemics, natural disasters, or major disruptions, provisions may be made to accommodate participants who are unable to attend onsite study visits

for scheduled assessments and dispensation of mavacamten. Guidance on participant management in these situations is outlined in [Appendix 4](#).

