Participants must use highly effective birth control from 43 months after last dose of investigational medicinal product	Align with IB Ed 8.1	Synopsis, Section 5.2., Section 8.2.2., Section 8.2.3.
The following abbreviations were deleted: ECHO = echocardiogram ID = identification MAD = multiple ascending dose SAD = single ascending dose	These abbreviations are not used in the body of protocol amendment 4	List of Abbreviations
Updated information on completed and ongoing studies with mavacamten and number of participants enrolled	Align with IB Ed 8.1	Section 1.2.

Summary of Change	Reason for Change	Section(s)
Updated text describing clinical benefits and known risks of mavacamten	Align with IB Ed 8.1	Section 1.3.
Updated Study Schema to include telehealth visit at Week 222 and Early Termination	To align with Table 3	Study Schema
Deleted IMP Compliance for Week 222	Week 222 is now a telehealth visit	Table 3
Updated text on symptomatic overdose	Align with IB Ed 8.1	Section 7.6.
Added term dizziness as a likely risk of mavacamten use	Align with IB Ed 8.1	Section 8.1.
Updated so participants will report pregnancies any time from first dose to 43 months after last dose of mavacamten	Align with IB Ed 8.1	Section 8.2.3.
Participants must abstain from blood or plasma donation for 34 months after the final study visit	Align with data on long terminal elimination half-life of mavacamten in IB Ed 8.1	Section 9.4.

PROTOCOL SYNOPSIS

Title	An Open-label Extension Study of Mavacamten (MYK-461) in Adults with Symptomatic Obstructive Hypertrophic Cardiomyopathy Previously Enrolled in Study MYK-461-004 (PIONEER-HCM)
Study Number	MYK-461-008
Study Phase	2
Number of Centers	Up to 5 sites in the United States
Primary Objective	To assess the long-term safety and tolerability of mavacamten in individuals with symptomatic obstructive hypertrophic cardiomyopathy (oHCM)
Secondary Objectives	To assess in individuals with symptomatic oHCM the long-term effects of mavacamten on: 
 • Left ventricular outflow tract (LVOT) obstruction • Functional capacity • oHCM symptoms
Pharmacokinetic Objective	To perform population pharmacokinetics (PK) analyses in individuals with symptomatic oHCM receiving mavacamten

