4.1. Study Duration

The expected study duration is approximately 264 weeks: up to 4 weeks for Screening, a 252-week (5-year) treatment period, and an 8-week posttreatment follow-up period, or until mavacamten becomes commercially available. If mavacamten clinical development is discontinued, this study will be terminated. The EOS is defined as the date of the last observation of the last participant.

Table 2 Schedule of Assessments – Screening Through Year 2

Assessment ^a	Year 1												Year 2									
	Screening Days -28 to -1	Day 1	Wk 4	Wk 6	Wk 8	Wk 12	Wk 18	Wk 24	Wk 30	Wk 36	Wk 42	Wk 48	Wk 54	Wk 60	Wk 66	Wk 72	Wk 78	Wk 84	Wk 90	Wk 96	Wk 102	
Telehealth Visit ^b							X		X		X		X		X		X		X		X	
Informed consent	X																					
Medical history ^c	X																					
Vital signs ^d	X	X	X	X	X	X		X		X		X		X		X		X		X		
AEs/SAE ^e	X	X	X	X	X	X	X	X	X	X	X	X	X	X	X	X	X	X	X	X	X	
Concomitant therapy	X	X	X	X	X	X	X	X	X	X	X	X	X	X	X	X	X	X	X	X	X	
Physical examination ^f	X	X	X		X	X		X		X		X		X		X		X		X		
ECG ^g	X	X	X		X	X		X		X		X		X		X		X		X		
Resting TTE ^h	X		X		X	X		X		X		X				X				X		
Stress TTE ^h	X		X									X				X						
Mavacamten 5 mg daily		←→																				
Dosing		←→																				
Dose adjustment up to target ⁱ			←→																			
IMP compliance check ^j			X	X	X	X		X		X		X		X		X		X		X		
Hepatitis panel and HIV test	X																					
PK sample ^k			X		X			X		X		X		X		X				X		
Chemistry	X		X			X				X				X		X				X		
Hematology	X		X			X				X				X		X				X		
NT-proBNP ^l	X	X	X		X	X		X		X		X		X		X				X		
FSH ^m	X																					
Pregnancy test (β-hCG) ⁿ	X	X	X		X	X	X	X	X	X	X	X	X	X	X	X	X	X	X	X	X	
NYHA class, KCCQ	X	X	X		X			X				X				X				X		

Abbreviations: β-hCG, beta-human chorionic gonadotropin; AE, adverse event; BP, blood pressure; ECG, electrocardiogram; eCRF, electronic case report form; FSH, follicle-stimulating hormone; HCM, hypertrophic cardiomyopathy; HIV, human immunodeficiency virus; IMP, investigational medical product; KCCQ, Kansas City Cardiomyopathy Questionnaire; LVOT, left ventricular outflow tract; NT-proBNP, N-terminal pro B-type natriuretic peptide; NYHA, New York Heart Association; PK, pharmacokinetic(s); SAE, serious adverse event; TTE, transthoracic echocardiography; Wk, week.

Note: The Week 4 visit has a visit window of ± 4 days; all remaining visits have a window of ± 7 days.

Table 2 Schedule of Assessments – Screening Through Year 2 (Continued)

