- ^f At Screening, a complete physical examination will be conducted, including a neurological examination (gross motor and deep tendon reflexes), height and weight, and assessment of the following: general appearance, skin, head and neck, mouth, lymph nodes, thyroid, abdomen, musculoskeletal, cardiovascular, neurological, and respiratory systems. At all other onsite visits, an abbreviated cardiopulmonary physical examination will be conducted, with other systems assessed as directed by interval history; weight will also be recorded at all physical examinations.
- ^g A 12-lead ECG will be performed after 10 minutes of rest. On Day 1, ECG will be performed predose.
- ^h Instantaneous peak LVOT gradient (baseline) and provoked peak LVOT gradient (Valsalva maneuver) will be assessed. Ejection fraction (2-dimensional), left ventricular fractional shortening, global longitudinal strain by speckle tracking, and velocity timing interval will be analyzed. Resting TTE should be performed prior to stress echocardiography. All stress echocardiograms should include a 4-hour fast prior to exercise. If the post-exercise LVOT gradient is measured ≥ 50 mmHg, further dose adjustment may be considered and discussed with the MyoKardia Medical Monitor. If dose adjustment occurs at Week 24 or beyond, a follow-up visit (to mirror Week 8 assessments) should be scheduled 4 weeks later (± 7 days) to include a TTE assessment. All stress echocardiography visits will be conducted in the clinic.
- ⁱ Dose adjustment is optional. Dose adjustments beyond the Target Dose may only be exceeded for each given participant following discussion between the Investigator and the MyoKardia Medical Monitor. Lower doses are permissible.
- ^j Compliance with study drug will be monitored by capsule count at each clinic visit.
- ^k A blood sample will be collected prior to dosing for assessment of trough study drug plasma concentrations. On days of visits, participants should not take their daily dose prior to visit. Study drug will be administered on site to facilitate collection of this sample.
- ^l The blood draw for NT-proBNP will occur prior to stress echocardiography.
- ^m FSH testing at Screening for postmenopausal females to confirm postmenopausal status.
- ⁿ Pregnancy test (serum or urine) for females of childbearing potential, based on standard at institution. A urine pregnancy test is performed at home every 4 weeks when no clinic visit is scheduled.

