11. STATISTICAL METHODS

11.1. Determination of Sample Size

No statistical hypothesis testing will be performed in this long-term extension study. Up to 20 individuals with symptomatic oHCM who completed Study MYK-461-004 will be enrolled.

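### After the Week 6 dose increase, one trough is scheduled at Week 8 and none until Week 24, so the concentration stop criterion goes unchecked for 16 weeks and the Week 8 value may precede steady state.

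*Combined protocol and SAP*

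**What the plan says.** Everyone starts on 5 mg. Section 4 then states: "The dose may be increased at Week 6 to the Target Dose provided in" Table 1. The increase is barred if, at Week 4, LVEF is below 55%, the post-exercise gradient is below 30 mmHg, the trough exceeds 350 ng/mL, or the investigator judges it unwarranted. The Target Dose is defined by a steady-state trough of about 250 to 500 ng/mL.

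The Table 2 PK row is marked at Weeks 4, 8, 24, 36, 48, 60, 72 and 96. Footnote k describes the sample: "A blood sample will be collected prior to dosing for assessment of trough study drug plasma concentrations". Visits from Week 6 on have a ±7-day window.

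Two provisions cover follow-up after a dose change:

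- Section 4 and the Synopsis, for any adjustment: participants "should return to the clinic approximately 28 days later (± 7 days) for an unscheduled visit with resting TTE to confirm safety".
- Table 2 footnote h, for later adjustments: "If dose adjustment occurs at Week 24 or beyond, a follow-up visit (to mirror Week 8 assessments) should be scheduled 4 weeks later". Week 8 includes a PK sample.

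The temporary-discontinuation criteria in Sections 4 and 7.5 have three limbs: concentration of 1000 ng/mL or more, LVEF below 50%, and QTcF limits. The protocol gives no half-life. The Amendment 4 summary of changes describes it only in words, as the reason for a blood-donation restriction: "Align with data on long terminal elimination half-life of mavacamten in IB Ed 8.1".

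**The concern.** The Week 6 step doubles or triples the dose and is the one increase the protocol plans in advance. Its only concentration check before Week 24 is nominally 14 days later. If the drug accumulates slowly, that sample understates the trough the new dose will reach, and no later sample is scheduled for 16 weeks. The concentration limb cannot act where nothing is measured, and the 250 to 500 ng/mL premise behind each Target Dose is not verified over that time. Week 12 has TTE, ECG and NT-proBNP but no concentration from the same visit.

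The two follow-up provisions also leave the planned step with less concentration follow-up than an optional change at Week 24 or later. The Amendment 2 log shows that the sponsor regards trough sampling as necessary for titration: it added PK at Weeks 36 and 60 for that reason. Nothing was added between Weeks 8 and 24.

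**Working it through.** The study is descriptive (Section 11.1), so there is no sample-size or power figure to reproduce. The check concerns timing and accumulation.

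**Inputs from the protocol**
- Table 1 Target Doses: six at 5 mg, eleven at 10 mg, three at 15 mg. Above 5 mg: 11 + 3 = 14 of 20.
- PK samples at Weeks 4, 8 and 24, with none at Weeks 6, 12 or 18.
- Highest Week 4 trough that still allows the increase: 350 ng/mL.
- Concentration stop criterion: 1000 ng/mL or more.

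**Assumptions, not in the protocol**
- Half-life h between 2 and 24 days.
- One-compartment, dose-proportional kinetics.
- Visits on their nominal days unless stated.

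**Step 1: timing**
- Week 8 to Week 24 is 16 weeks without a scheduled sample. Week 6 to Week 24 is 18 weeks.
- Week 8 is nominally 14 days after the increase. With the windows, the shortest interval is 0 days (Day 42 + 7 = Day 49 = Day 56 − 7) and the longest is 28 days (Day 35 to Day 63).

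**Step 2: share of the change to the new steady state**

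Share after t days = 1 − 2^(−t/h).

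| h (days) | Week 8 (14 d) | Week 12 (42 d) | Week 24 (126 d) |
|---|---|---|---|
| 3 | 96% | 100% | 100% |
| 5 | 86% | 99.7% | 100% |
| 7 | 75% | 98% | 100% |
| 14 | 50% | 87.5% | 99.8% |
| 24 | 33% | 70% | 97% |

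Week 8 falls below 90% when h exceeds 14 × ln 2 / ln 10 = 4.2 days.

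**Step 3: worst case within the 350 ng/mL limit**

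With a Week 4 trough of 350 ng/mL on 5 mg:
- Steady state on 5 mg: S5 = 350 / (1 − 2^(−28/h)).
- Trough at Week 6: C6 = S5 × (1 − 2^(−42/h)).
- New steady state: S = 3 × S5 on 15 mg, or 2 × S5 on 10 mg.
- Trough t days after the increase: S − (S − C6) × 2^(−t/h).

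Example, h = 7 and 15 mg: S5 = 350/0.9375 = 373.3; C6 = 373.3 × 0.9844 = 367.5; S = 1120. Week 8 = 1120 − 752.5 × 0.25 = 932. Week 12 = 1120 − 752.5 × 0.0156 = 1108.

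Step to 15 mg (ng/mL):

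| h (days) | Week 8 | Week 12 | Steady state | Week 8 detects? |
|---|---|---|---|---|
| 3 | 1024 | 1052 | 1052 | yes |
| 5 | 969 | 1070 | 1072 | no |
| 7 | 932 | 1108 | 1120 | no |
| 14 | 904 | 1276 | 1400 | no |
| 24 | 926 | 1462 | 1893 | no |

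The switch from detected to missed lies just under 4 days (at h = 4: Week 8 is 996, steady state 1058).

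Step to 10 mg: steady state is 933 at h = 14, so the criterion is not reached. It reaches 1000 only when 700 / (1 − 2^(−28/h)) = 1000, that is h = 28 × ln 2 / ln(1/0.3) = 16 days. At h = 21, Week 8 is 704, Week 12 is 979 and steady state is 1161. At h = 24, the values are 716, 1019 and 1262.

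**The case against.** The strongest reply is that safety does not rest on concentration alone. TTE and ECG are scheduled at Weeks 8 and 12, and the 28-day visit adds a TTE at about Week 10, so the LVEF and QTcF limbs are checked repeatedly. Section 1.3 describes toxicity as exaggerated pharmacology and cites another extension study that titrated without plasma concentrations. This stands, and it limits the point to the concentration limb. Unscheduled laboratory tests are allowed at the investigator's discretion, but PK is not named among them.

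Second, the worst case is unlikely by design. Target Doses were set individually for 250 to 500 ng/mL, so 1000 is twice the top of that range. The 350 ng/mL limit screens out the highest exposures, and the investigator may decline the increase. This also stands: the table shows what the rules permit, not what is expected.

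Third, a reader might infer that Week 8 is definitely before steady state, that the new steady state goes unchecked for 18 weeks, or that all 14 participants could pass 1000 ng/mL unseen. The protocol supports none of these. The word long in an amendment log is not a half-life. The 18 weeks run from the increase and include the Week 8 sample and the approach to steady state. Under the 350 ng/mL limit, the 10 mg step stays below 1000 at half-lives up to 14 days.

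Fourth, PK/PD modelling uses sparse data, possibly pooled with other studies, and the PK/PD population needs only one coincident pair. The missing Week 12 concentration is therefore a minor loss to that analysis.

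**Conclusion.** The point holds as a limited gap that is cheap to close. Three facts rest on the protocol alone: 16 weeks without a scheduled concentration after Week 8; a Week 8 sample that may fall anywhere from 0 to 28 days after the increase; and a 28-day visit that names no PK sample, whereas footnote h gives later adjustments a visit that includes one.

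The consequence is conditional. It rests on the assumed half-life range and on dose-proportional one-compartment kinetics. Above about 4 days, the Week 8 trough is not a steady-state value, and in the worst permitted case on 15 mg (3 of 20 rows) it reads below 1000 ng/mL while steady state lies above. On 10 mg this needs a half-life above about 16 days. At about 4 days or less, Week 8 is an adequate check when drawn on its nominal day. The loss of exposure verification at the new dose applies to up to 14 participants.

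**What to change.** 1. Add a predose PK sample at Week 12 in Table 2, using the blood draw already scheduled there for chemistry, hematology and NT-proBNP. In the worst case above, it reads over 1000 ng/mL for every half-life tabulated on 15 mg. It would not settle every case: 10 mg with a 21-day half-life still reads 979.
2. Reconcile the 28-day visit in Section 4 and the Synopsis with Table 2 footnote h, and say explicitly whether PK is drawn after adjustments before Week 24.
3. State the half-life or time to steady state in the protocol, so that readers can judge the Week 8 value.
4. In the PK summaries, do not treat the Week 8 concentration as a steady-state trough for participants adjusted at Week 6.

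The cost is one extra tube and assay per participant, one mark in Table 2 and a few lines of text. No visit is added, and no dose or stopping rule changes.
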